4.4 CONCOMITANT THERAPY AND PROHIBITED FOOD

Details on concomitant therapy, prohibited food, and additional restrictions for each treatment arm are provided in the respective appendix for that treatment arm, as outlined in [Table 4](#) for Stage 1 and [Table 5](#) for Stage 2.

4.5 STUDY ASSESSMENTS

A schedule of activities to be performed during the study is provided for each treatment arm (see [Appendix 7](#) and [Appendix 8](#)). All activities must be performed and documented for each patient. Patients will be closely monitored for safety and tolerability throughout the study. Patients should be assessed for toxicity prior to each dose; dosing will occur only if the clinical assessment and local laboratory test values are acceptable.

4.5.1 Informed Consent Forms and Screening

Written informed consent for participation in the study must be obtained before performing any study-related procedures (including screening evaluations). Informed Consent Forms for enrolled patients and for patients who are not subsequently enrolled will be maintained at the study site.

Written informed consent must also be obtained before performing screening evaluations for Stage 2.

Screening evaluations for Stage 1 and Stage 2 are to be performed within 28 days prior to initiation of study treatment (Day 1). All screening evaluations must be completed and reviewed to confirm that patients meet all eligibility criteria before enrollment (see [Appendix 6](#) for the schedule of activities for Stage 1 screening).

Patients who fail their first screening for study eligibility (Stage 1 or Stage 2) may qualify for two re-screening opportunities (for a total of three screening opportunities per patient) at the investigator's discretion. Patients must re-sign the consent form prior to re-screening. Results of standard-of-care tests or examinations performed prior to obtaining informed consent and within a specified time prior to Day 1 (see the schedule of activities for each arm in [Appendix 7](#) and [Appendix 8](#)) may be used; such tests do not need to be repeated for screening or re-screening.

4.5.2 Medical History, Molecular Profile, Concomitant Medication, and Demographic Data

Medical history, including clinically significant diseases, surgeries, cancer history (including prior cancer therapies and procedures), reproductive status, smoking history, and use of alcohol and drugs of abuse, will be recorded at baseline. A patient's molecular profile for GC and GEJC, if available, will be recorded at screening and whenever updated information becomes available during the study. In addition, all medications (e.g., prescription drugs, over-the-counter drugs, vaccines, herbal or homeopathic remedies, nutritional supplements) used by the patient within a specified time prior to initiation of study treatment will be recorded (as outlined for each arm in [Appendix 7](#) and [Appendix 8](#)). At the time of each follow-up physical examination, an interval medical history should be obtained and any changes in medications and allergies should be recorded. Demographic data will include age, sex, and self-reported race/ethnicity.

4.5.3 Physical Examinations

A complete physical examination, performed at screening and other specified visits, should include an evaluation of the head, eyes, ears, nose, and throat, and the cardiovascular, dermatologic, musculoskeletal, respiratory, gastrointestinal, genitourinary, and neurologic systems. Any abnormality identified at baseline should be recorded on the General Medical History and Baseline Conditions electronic Case Report Form (eCRF).

Limited, symptom-directed physical examinations should be performed at specified postbaseline visits and as clinically indicated. Changes from baseline abnormalities should be recorded in patient notes. New or worsened clinically significant abnormalities should be recorded as adverse events on the Adverse Event eCRF.

During visits when a patient will undergo a tumor assessment, the physical examination should include an evaluation of the presence and degree of enlarged lymph nodes, hepatomegaly, and splenomegaly.

Weight will be recorded at specified timepoints during the study.

4.5.4 Vital Signs

Vital signs will include measurements of respiratory rate, pulse rate, and systolic and diastolic blood pressure while the patient is in a seated position, pulse oximetry, and temperature.

Vital signs should be measured at other specified timepoints as outlined for each arm in the schedule of activities in [Appendix 7](#) and [Appendix 8](#).

4.5.5 Electrocardiograms

An ECG is required at screening and as outlined in the schedule of activities. ECGs for each patient should be obtained from the same machine wherever possible. Lead placement should be as consistent as possible. It is recommended that patients be resting in a supine position for at least 10 minutes prior to ECG recording.

For safety monitoring purposes, the investigator must review, sign, and date all ECG tracings. Paper copies of ECG tracings will be kept as part of the patient's permanent study file at the site. Any morphologic waveform changes or other ECG abnormalities must be documented on the eCRF.

4.5.6 Tumor and Response Evaluations

Patients will undergo tumor assessments every 6 weeks (± 1 week) during the first 48 weeks (from Day 1 of Cycle 1) and then every 12 weeks (± 2 weeks) thereafter, regardless of dose delays until confirmed radiographic disease progression, except in the case of patients who continue treatment after radiographic disease progression; such patients will undergo tumor assessments every 6 weeks (± 1 week) until loss of clinical benefit as determined by the investigator (see Section [3.1.2](#) for details). Thus, tumor assessments are to continue according to schedule in patients who discontinue treatment for reasons other than loss of clinical benefit, even if they start a new non-protocol-specified anti-cancer therapy. At the investigator's discretion, tumor assessments may be repeated at any time if progressive disease is suspected.

Baseline tumor assessments for Stage 2 must be performed within 28 days prior to initiation of Stage 2 treatment (i.e., Day 1 of Cycle 1). Tumor assessments performed prior to or at the time of unacceptable toxicity or loss of clinical benefit during Stage 1 may serve as baseline assessments for Stage 2, provided the tumor assessments are performed within 28 days prior to initiation of Stage 2 treatment.

All measurable and/or evaluable lesions should be assessed and documented at screening (in both Stage 1 and Stage 2). Brain metastases treated with radiotherapy or surgery will not be considered measurable or evaluable but will be documented at screening as a site of metastatic disease. Tumor assessments performed as standard of care prior to obtaining informed consent and within 28 days prior to initiation of study treatment do not have to be repeated at screening.

Screening assessments must include CT scans (with IV contrast; with or without oral contrast) or magnetic resonance imaging (MRI) scans (with IV contrast) of the chest, abdomen, and pelvis. A spiral CT scan of the chest may be obtained but is not a requirement. If a CT scan with contrast is contraindicated (i.e., in patients with contrast allergy or impaired renal clearance), a non-contrast CT scan of the chest may be performed and MRI scans (with IV contrast, if feasible) of the abdomen and pelvis should be performed. Bone scans, CT or MRI scans of the neck, and CT or MRI scans of the brain should also be performed if clinically indicated. At the investigator's discretion, other methods of assessment of measurable disease as per RECIST v1.1 may be used.

If a CT scan for tumor assessment is performed in a positron emission tomography/CT scanner, the CT acquisition must be consistent with the standards for a full-contrast diagnostic CT scan.

All measurable and/or evaluable lesions identified at baseline should be re-assessed at subsequent tumor evaluations according to the schedule described above. Brain metastases identified at baseline that have been treated with radiotherapy or surgery will not be considered measurable or evaluable unless there is suspected disease progression in the brain (i.e., the patient becomes symptomatic). Thus, subsequent head scans are not required unless clinically indicated. The same radiographic procedures used to assess disease sites at screening should be used for subsequent tumor assessments (e.g., the same contrast protocol for CT scans). Tumor assessments must be continued after disease progression per RECIST v1.1 for patients who receive treatment beyond progression. This includes continued measurement of target lesions, evaluation of non-target lesions (including monitoring for further worsening of any non-target lesions that have shown unequivocal progression), and evaluation of any newly identified lesions (including measurements, if lesions are measurable) at all subsequent assessments.

Overall response at a single timepoint will be assessed by the investigator using RECIST v1.1 (see [Appendix 1](#)). Assessments should be performed by the same evaluator, if possible, to ensure internal consistency across visits. Results must be reviewed by the investigator prior to treatment administration.

and/or uterus) or another cause as determined by the investigator (e.g., Müllerian agenesis).

- Urinalysis includes pH, specific gravity, glucose, protein (or albumin), ketones, and blood; dipstick permitted

The following samples will be sent to one or several central laboratories or to the Sponsor or a designee for analysis:

- Serum samples for PK analysis through use of validated assays (see [Appendix 7](#) and [Appendix 8](#))
- Serum samples for immunogenicity analysis through use of validated assays (see [Appendix 7](#) and [Appendix 8](#))
- *Blood*, serum, plasma, and WBC samples for biomarker analysis and biomarker assay development (see [Appendix 7](#) and [Appendix 8](#))

Plasma and WBC will be isolated from blood at central laboratory.

- Archival or newly collected tumor tissue sample collected at baseline for determination of PD-L1 and TIGIT expression, tumor-infiltrating lymphocytes, microsatellite instability (MSI) status, EBV infection, gene expression profiling, and other biomarkers

Baseline tumor tissue samples from the primary lesion or a metastatic lesion will be collected from all patients, preferably by means of a biopsy performed at study entry. If a biopsy is not deemed feasible by the investigator, archival tumor tissue may be submitted, provided that the patient has not received any systemic anti-cancer therapy and that the tissue was obtained from a previous surgery or biopsy performed within 6 months prior to enrollment.

A representative FFPE tumor specimen 7-18 slides (18 slides highly preferred) containing unstained, freshly cut, serial sections must be submitted along with an associated pathology report.

Tumor tissue should be of good quality based on total and viable tumor content. Samples must contain a minimum of 50 viable tumor cells that preserve cellular context and tissue architecture regardless of needle gauge or retrieval method. Samples collected via resection, core-needle biopsy (16–18 gauge preferred, at least three cores and embedded in a single paraffin block), or excisional, incisional, punch, or forceps biopsy are acceptable. Fine-needle aspiration (defined as samples that do not preserve tissue architecture and yield cell suspension and/or smears), brushing, cell pellets from pleural effusion, and lavage samples are not acceptable. Tumor tissue from bone metastases that have been decalcified is not acceptable.

- Tumor tissue sample collected during Stage 1 at the time of unacceptable toxicity or loss of clinical benefit as determined by the investigator (see [Section 3.1.2](#) for details), if deemed clinically feasible by the investigator, for biomarkers analysis

Biopsies should be performed within 40 days after determination of unacceptable toxicity, disease progression, or loss of clinical benefit, or prior to the next anti-cancer therapy, whichever is sooner. Samples collected by means of resection, core-needle biopsy (at least three cores preferred), or excisional, incisional, punch, or forceps biopsy are preferred.

Biomarker research may include, but will not be limited to, analysis of genes or gene signatures associated with tumor molecular subtype and tumor immunobiology, PD-L1, expression of targets specific to each drug combination (e.g., TIGIT), EBV, tumor mutation load, MSI status, lymphocyte subpopulations, T cell–receptor repertoire, or cytokines. Research may involve DNA or RNA extraction, analysis of somatic mutations, and use of NGS (including WES). Biomarker sample collections and research are applicable only after approval from the local regulatory authorities.

For sampling procedures, storage conditions, and shipment instructions, see the laboratory manual.

Biological samples will be destroyed no later than the time of completion of the final Clinical Study Report, with the following exceptions:

- Serum samples collected for PK or immunogenicity analysis may be needed for additional immunogenicity characterization and for PK or immunogenicity assay development and validation; therefore, these samples will be destroyed no later than 5 years after the final Clinical Study Report has been completed.
- Plasma, serum, blood, tumor tissue, and stool samples collected for biomarker research will be destroyed no later than 5 years after the final Clinical Study Report has been completed.
- For patients who are not enrolled, remaining archival tissue specimens will be returned to the site no later than 6 months after eligibility determination.

When a patient withdraws from the study, samples collected prior to the date of withdrawal may still be analyzed, unless the patient specifically requests that the samples be destroyed or local laws require destruction of the samples. However, if samples have been tested prior to withdrawal, results from those tests will remain as part of the overall research data.

Data arising from sample analysis, including data on genomic variants, will be subject to the confidentiality standards described in Section [8.4](#).

The aggregate results of any conducted research will be available in accordance with the effective Sponsor policy on study data publication.

4.5.8 Optional Tumor Biopsies

Patients will be given the option of consenting to additional tumor biopsies. Patients who consent to optional biopsies will undergo tumor biopsy sample collection 8 weeks (± 7 days) after treatment initiation, if deemed clinically feasible by the investigator. In addition, patients who consent to optional biopsies may undergo additional biopsies during treatment at any other time at the investigator's discretion.

Samples collected by means of resection, core-needle biopsy (at least three cores preferred), or excisional, incisional, punch, or forceps biopsy are preferred. For sampling procedures, storage conditions, and shipment instructions, see the laboratory manual.

The Informed Consent Form will contain a separate section that addresses optional biopsies. A separate, specific signature will be required to document a patient's agreement to undergo optional biopsies.

The investigator should document whether or not the patient has given consent to participate and (if applicable) the date(s) of consent, by completing the Optional Biopsy Sample Informed Consent eCRF.

Samples may be used for biomarker analysis as described in Section 4.5.7. See Section 4.5.7 for details on sample storage, use of samples after patient withdrawal, confidentiality standards for data, and availability of data from biomarker analyses.

4.5.9 Optional Stool Samples

Patients will be given the option of consenting to provide stool samples. Patients who consent to providing optional stool samples will receive the collection device prior to baseline and the Day 1, Cycle 3 visit. For sampling procedures, storage conditions, and shipment instructions, see the laboratory manual. The Informed Consent Form will contain a separate section that addresses optional stool samples. A separate, specific signature will be required to document a patient's agreement to provide optional stool samples.

The investigator should document whether or not the patient has given consent to participate and (if applicable) the date(s) of consent, by completing the Optional Stool Sample Informed Consent eCRF. Samples may be used for biomarker research as described in Section 4.5.7. Refer to Section 4.5.7 for details on sample storage, use of samples after patient withdrawal, confidentiality standards for data, and availability of data from biomarker analyses.

4.6 TREATMENT, PATIENT, STUDY, AND SITE DISCONTINUATION

4.6.1 Study Treatment Discontinuation

Patients must permanently discontinue study treatment if they experience any of the following:

- Intolerable toxicity related to study treatment, including development of an immune-mediated adverse event determined by the investigator to be unacceptable given the individual patient's potential response to therapy and severity of the event
- Any medical condition that may jeopardize the patient's safety if he or she continues study treatment
- Investigator or Sponsor determines it is in the best interest of the patient
- Use of another non-protocol-specified anti-cancer therapy
- Pregnancy
- Loss of clinical benefit as determined by the investigator after an integrated assessment of radiographic and biochemical data, local biopsy results (if available), and clinical status (e.g., symptomatic deterioration such as pain secondary to disease) (see Section [3.1.2](#) for details)

The primary reason for study treatment discontinuation should be documented on the appropriate eCRF.

Patients will return to the clinic for a treatment discontinuation visit ≤ 30 days after the final dose of study treatment. The visit at which response assessment shows progressive disease or loss of clinical benefit may be used as the treatment discontinuation visit. Patients who discontinue study treatment for any reason other than progressive disease or loss of clinical benefit will continue to undergo tumor response assessments as outlined in the schedule of activities provided for each arm in [Appendix 7](#) and [Appendix 8](#).

After treatment discontinuation, information on survival follow-up and initiation of a new anti-cancer therapy will be collected by means of telephone calls, patient medical records, and/or clinic visits approximately every 3 months (± 2 weeks) or more frequently until death (unless the patient withdraws consent or the Sponsor terminates the study). If a patient requests to be withdrawn from follow-up, this request must be documented in the source documents and signed by the investigator. If the patient withdraws from the study, the study staff may use a public information source (e.g., county records) to obtain information about survival status only. For an experimental arm, in which all patients discontinued treatment and passed the safety follow-up window, as well as approximately 80% of patients discontinued the study, the Sponsor may conclude the arm (the remaining approximately 20% of patients will be discontinued from the study).

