2. OBJECTIVES AND ENDPOINTS

This study will evaluate the efficacy, safety, and pharmacokinetics of multiple treatment combinations in patients with advanced GC or GEJC. Specific objectives and corresponding endpoints for the study are outlined below for Stage 1 (see Table 2) and Stage 2 (see Table 3).

Table 2 Objectives and Corresponding Endpoints for Stage 1

Primary Efficacy Objective	Corresponding Endpoint

 To evaluate the efficacy of treatment combinations during Stage 1 	
 ORR, defined as the proportion of patients with a complete response or a partial response on two consecutive occasions ≥ 4 weeks apart during Stage 1, as determined by the investigator according to RECIST v1.1
Secondary Efficacy Objective	Corresponding Endpoints

 To evaluate the efficacy of treatment combinations during Stage 1 	
 PFS after randomization, defined as the time from randomization to the first occurrence of disease progression or death from any cause (whichever occurs first) in Stage 1, as determined by the investigator according to RECIST v1.1 OS after randomization, defined as the time from randomization to death from any cause, regardless of stage OS at specific timepoints (e.g., 6 and 12 months) DOR, defined as the time from the first occurrence of a documented objective response to disease progression or death from any cause (whichever occurs first) in Stage 1, as determined by the investigator according to RECIST v1.1 Disease control rate, defined as the proportion of patients with stable disease for ≥ 12 weeks or a complete or a partial response, as determined by the investigator according to RECIST v1.1
Safety Objective	Corresponding Endpoint

 To evaluate the safety of treatment combinations during Stage 1 	
 Incidence and severity of adverse events, with severity of all events graded according to NCI CTCAE v5.0 and severity for CRS also graded according to the ASTCT CRS Consensus Grading Scale

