6.4.2 Secondary Efficacy Endpoints

The secondary efficacy endpoints are PFS, OS, OS at specific timepoints (e.g., 6 and 12 months), duration of response (DOR), and disease control during Stage 1, as defined in Section 2 (see Table 2). PFS, DOR, and disease control will be determined by the investigator according to RECIST v1.1.

DOR will be derived for efficacy-evaluable patients with a complete response or a partial response.

For patients who do not have documented disease progression or die, PFS and DOR will be censored at the day of the last tumor assessment.

Patients who are still alive at the time of OS analysis will be censored at the last date they were known to be alive.

The method will be used to estimate the median for PFS, OS, and DOR, with 95% CIs constructed through use of the method. The OS rate at specific timepoints will also be estimated using the method, with 95% CIs calculated based on for variance.

Disease control rate (the proportion of patients with stable disease for ≥ 12 weeks, a partial response, or a complete response) will be calculated for each treatment arm, with 95% CIs estimated using the [REDACTED].

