Appendix 1: Response Evaluation Criteria in Solid Tumors, Version 1.1 (RECIST v1.1)

having "symptomatic deterioration." Every effort should be made to document objective progression even after discontinuation of treatment. Symptomatic deterioration is not a descriptor of an objective response; it is a reason for stopping study therapy. The objective response status of such patients is to be determined by evaluation of target and non-target lesions as shown in [Table 1](#).

For equivocal findings of progression (e.g., very small and uncertain new lesions; cystic changes or necrosis in existing lesions), treatment may continue until the next scheduled assessment. If at the next scheduled assessment, progression is confirmed, the date of progression should be the earlier date when progression was suspected.

REFERENCES

Appendix 2

ECOG Performance Status Scale

Grade	Description
0	Fully active; able to carry on all pre-disease performance without restriction.
1	Restricted in physically strenuous activity but ambulatory and able to carry out work of a light or sedentary nature (e.g., light housework or office work).
2	Ambulatory and capable of all self-care but unable to carry out any work activities. Up and about >50% of waking hours.
3	Capable of only limited self-care; confined to a bed or chair >50% of waking hours.
4	Completely disabled. Cannot carry on any self-care. Totally confined to bed or chair.
5	Dead.

ECOG=Eastern Cooperative Oncology Group.

Appendix 3

Preexisting Autoimmune Diseases and Immune Deficiencies

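### Scan rules conflict for patients who stop treatment for loss of clinical benefit without RECIST progression, so each arm's PFS and DOR can be biased upward

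*Combined protocol and SAP*

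**What the plan says.** **How long scans run.** The opening sentence of Section 4.5.6 has scans continue "regardless of dose delays until confirmed radiographic disease progression, except in the case of patients who continue treatment after radiographic disease progression"; only that excepted group is scanned until loss of clinical benefit. The next sentence draws a different line: "tumor assessments are to continue according to schedule in patients who discontinue treatment for reasons other than loss of clinical benefit". Section 4.6.1 agrees with the second sentence: "Patients who discontinue study treatment for any reason other than progressive disease or loss of clinical benefit will continue to undergo tumor response assessments". Footnote t of the activity schedules in Appendix 7 (Table 4) and Appendix 8 (Table 5) repeats the 4.5.6 text, so the exemption stands in four places.

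**What loss of clinical benefit is.** Section 4.6.1 bases it on the investigator's "integrated assessment of radiographic and biochemical data, local biopsy results (if available), and clinical status (e.g., symptomatic deterioration such as pain secondary to disease". Section 4.6.1 also lists it separately from progressive disease. Appendix 1 says: "Symptomatic deterioration is not a descriptor of an objective response; it is a reason for stopping study therapy". For these patients it adds: "Every effort should be made to document objective progression even after discontinuation of treatment".

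**What PFS counts.** Section 2 gives "PFS after randomization, defined as the time from randomization to the first occurrence of disease progression or death from any cause", limited to Stage 1 and judged by the investigator under RECIST v1.1. Section 6.4.2 adds: "For patients who do not have documented disease progression or die, PFS and DOR will be censored at the day of the last tumor assessment". It has no rule or sensitivity analysis for loss of clinical benefit. Survival is followed about every 3 months until death (Section 4.6.1).

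**The concern.** A patient can be taken off treatment because the investigator judges that it is failing, without any scan that meets RECIST progression. The exemption then releases that patient from scheduled scans. Two outcomes remain. If a later death is observed and counted, the PFS event is dated at death rather than at progression. If not, the patient is censored at the last scan for a reason tied to poor prognosis. Both push the arm's PFS curve up. DOR follows the same censoring rule, so the same argument applies to responders.

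PFS and DOR are the plan's main evidence on durability in a signal-finding study. An upward shift could make an arm look better than it is against outside data. The study is open label, so the rate of such judgements could also differ between arms.

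**Working it through.** **Planning figures.** The plan states no PFS assumption, event count or power. Its only planning figure is 40–90 patients, which is reproduced at 1:1 allocation: 2 × 20 = 40 and 2 × (20 + 25) = 90. Nothing below depends on it.

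**Inputs, all assumed except the scan interval.**
- Exponential time to failure with median m = 7.0 months. This lies within the 6.1–7.7 months that Section 1.2 cites from a first-line trial.
- A share f of failures is clinical only: 5%, 10% or 20%.
- Median survival d after failure of 2, 4 or 6 months.
- Data cutoff spread evenly over 12–24 months.
- Scans every 6 weeks (Section 4.5.6).
- No unscheduled scan documents progression in the clinical-only group.

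**Step 1: the plan as written, deaths counted.** Clinical-only failures are events at death if death precedes the cutoff; otherwise they are censored at the last scan. Simulated Kaplan-Meier medians in months:

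| f | d = 2 | d = 4 | d = 6 | Excess over 7.0 |
|---|---|---|---|---|
| 5% | 7.16 | – | 7.31 | 2% to 4% |
| 10% | 7.35 | 7.55 | 7.61 | 5% to 9% |
| 20% | 7.65 | 8.11 | 8.26 | 9% to 18% |

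Repeat runs agree to within 0.1 month.

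Closed-form check with complete follow-up: S(t) = (1 − f)e^(−λt) + f[μe^(−λt) − λe^(−μt)]/(μ − λ), with λ = ln 2/7 = 0.0990 and μ = ln 2/d. For f = 0.10 and d = 4, μ = 0.1733. At t = 7.56 the bracketed ratio is (0.1733 × 0.4730 − 0.0990 × 0.2698)/0.0743 = 0.744, so S = 0.9 × 0.4730 + 0.1 × 0.744 = 0.500. The median is 7.56, against 7.55 simulated.

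**Step 2: which path dominates.** Of clinical-only failures before the cutoff, 68% (d = 6) to 92% (d = 2) are events at death. The rest are censored.

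**Step 3: if deaths after Stage 1 treatment do not count.** All these patients are censored, and the median is about m/(1 − f): 7.0/0.95 = 7.37, 7.0/0.90 = 7.78 and 7.0/0.80 = 8.75 months.

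**Step 4: a stricter benchmark.** The endpoint is RECIST progression, which may appear later than clinical failure. With an assumed lag of 1.4–2.8 months, the true median is itself above 7.0. Comparing like with like on d:
- 10%: from 7.35/7.21 (d = 2, lag 2.8) to 7.61/7.12 (d = 6, lag 1.4), or about +2% to +7%.
- 20%: from 7.65/7.38 to 8.26/7.27, or about +4% to +14%.

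**Step 5: 12-month PFS.** A second simulation used PFS medians of 6.1, 7.0 and 7.7 months, post-progression medians of 5.0, 6.0 and 6.7 months (the outer two from cited OS minus PFS: 11.1 − 6.1 and 14.4 − 7.7) and cutoffs at 12–36 months. With deaths counted, the excess is 1.2–1.3 percentage points at 5%, 2.3–2.6 at 10% and 4.8–5.3 at 20%.

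**Step 6: arm comparison.** In the same simulation with identical true PFS (7.0 months), the experimental-to-control event-rate ratio is 1.00 if both arms have 20%. With 10% experimental and 20% control it is 1.06 (deaths count) or 1.11 (all censored). Reversed, it is 0.95 or 0.90.

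**The case against.** **The protocol does not say flatly that scans stop.** The opening sentence of 4.5.6 runs them to confirmed radiographic progression, the same section allows a repeat assessment whenever progression is suspected, and Appendix 1 asks sites to keep documenting it. This stands: the defect is an inconsistency, and sites that follow the stricter text would narrow the gap. It does not remove the problem, because four explicit statements give a site good reason to stop scheduled scans.

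**The group may be small.** Loss of clinical benefit draws on radiographic data, and patients treated beyond RECIST progression already have their PFS event. Only those with no prior or concurrent RECIST progression matter. This stands; their share is unknown.

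**A reader might infer that PFS is overestimated through informative censoring.** The documents do not support that as stated. Survival is followed to death, so on these assumptions most such patients become late-dated events and only the remainder are informatively censored. The overestimate is also conditional on patients of this kind occurring. The late-death path is not fully secure either: PFS is defined within Stage 1, and Section 4.6.1 lets the sponsor close an experimental arm with about 20% of its patients still in follow-up.

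**The consequence is limited.** PFS is a secondary, descriptive endpoint, Section 6.1 disclaims hypothesis testing, and Section 6.4.2 plans per-arm medians without a hazard ratio. With 20–45 patients, the simulated standard deviation of a Kaplan-Meier median is about 1.5–2.2 months, larger than the shifts above. This stands on importance, but the shift is systematic and larger samples would not remove it.

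**Conclusion.** The scan rules contradict each other and must be reconciled. Where the exemption is followed, each arm's PFS can be biased upward, mainly by dating events at death and otherwise by prognosis-related censoring. DOR is exposed by the same rule, but its bias was not computed.

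On the stated assumptions, a 7.0-month median reads as about 7.2–7.3 months at 5% clinical-only failures, 7.3–7.6 at 10% and 7.6–8.3 at 20%. The excess is smaller if RECIST progression lags clinical failure, and larger if deaths after Stage 1 treatment do not count. The share itself is not in the documents.

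A reader might also infer that the rule creates a spurious difference between the arms. The documents do not support that: nothing in them indicates unequal rates, equal rates cancel, and reversing the rates reverses the sign. The primary endpoint, ORR, is largely unaffected. The change is worth making; confidence is moderate.

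**What to change.** 1. Reconcile Sections 4.5.6 and 4.6.1 and footnote t in Appendices 7 and 8 so that scheduled tumor assessments continue until RECIST v1.1 progression, death or withdrawal, whatever the reason for stopping treatment.
2. State in Section 6.4.2 whether deaths after Stage 1 treatment count as PFS events.
3. Add a PFS and DOR sensitivity analysis that counts loss of clinical benefit without RECIST progression as an event on the date it was determined, or on the treatment discontinuation date if the former is not captured.
4. Report the number of such patients by arm.

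**Cost.** Wording changes, a few further scheduled scans in a minority of patients, and one extra analysis. The reason for stopping treatment is already recorded on the eCRF, but nothing in the documents shows that the date of loss of clinical benefit is, so a new field may be needed. The sensitivity analysis relies on open-label investigator judgement and is supportive only.
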